5.2.3 Adverse Events of Special Interest (Immediately Reportable to the Sponsor)

Adverse events of special interest are required to be reported by the investigator to the Sponsor immediately (i.e., no more than 24 hours after learning of the event; see Section 5.4.2 for reporting instructions). Adverse events of special interest for this trial include the following:

- Cases of potential drug-induced liver injury that include an elevated ALT or AST in combination with either an elevated bilirubin or clinical jaundice, as defined by Hy's law (see Section 5.3.5.6)
- Suspected transmission of an infectious agent by the trial treatment, as defined below:

Any organism, virus, or infectious particle (e.g., prion protein transmitting transmissible spongiform encephalopathy), pathogenic or non-pathogenic, is considered an infectious agent. A transmission of an infectious agent may be suspected from clinical symptoms or laboratory findings that indicate an infection in a patient exposed to a medicinal product. This term applies only when a contamination of the trial treatment is suspected.

5.3 METHODS AND TIMING FOR CAPTURING AND ASSESSING SAFETY PARAMETERS

The investigator is responsible for ensuring that all adverse events (see Section 5.2.1 for definition) are recorded on the Adverse Event eCRF and reported to the Sponsor in accordance with instructions provided in this section and in Sections 5.4–5.6.

For each adverse event recorded on the Adverse Event eCRF, the investigator will make an assessment of seriousness (see Section 5.2.2 for seriousness criteria), severity (see Section 5.3.3), and causality (see Section 5.3.4).

5.3.1 Adverse Event Reporting Period

Investigators will seek information on adverse events at each patient contact. All adverse events, whether reported by the patient or noted by trial personnel, will be recorded in the patient's medical record and on the Adverse Event eCRF.

After informed consent has been obtained **but prior to initiation of trial treatment**, only serious adverse events caused by a protocol-mandated intervention (e.g., invasive procedures such as biopsies, discontinuation of medications) should be reported (see Section 5.4.2 for instructions for reporting serious adverse events).

After initiation of trial treatment, all adverse events will be reported until 28 days after the last dose of trial treatment (Follow-up Visit).

Instructions for reporting adverse events that occur after the adverse event reporting period are provided in Section 5.6.

5.3.2 Eliciting Adverse Event Information

A consistent methodology of non-directive questioning should be adopted for eliciting adverse event information at all patient evaluation time points. Examples of non-directive questions include the following:

"How have you felt since your last clinic visit?"

"Have you had any new or changed health problems since you were last here?"

5.3.3 Assessment of Severity of Adverse Events

The adverse event severity grading scale for the NCI CTCAE (v4.0) will be used for assessing adverse event severity. Table 4 will be used for assessing severity for adverse events that are not specifically listed in the NCI CTCAE.

Table 4 Adverse Event Severity Grading Scale for Events Not Specifically Listed in NCI CTCAE

Grade	Severity
1	Mild; asymptomatic or mild symptoms; clinical or diagnostic observations only; or intervention not indicated
2	Moderate; minimal, local, or non-invasive intervention indicated; or limiting age-appropriate instrumental activities of daily living ^a
3	Severe or medically significant, but not immediately life-threatening; hospitalization or prolongation of hospitalization indicated; disabling; or limiting self-care activities of daily living ^{b,c}
4	Life-threatening consequences or urgent intervention indicated ^d
5	Death related to adverse event ^d

NCI=National Cancer Institute; CTCAE=Common Terminology Criteria for Adverse Events.

Note: based on the most recent version of NCI CTCAE (v4.0), which can be found at:

http://ctep.cancer.gov/protocolDevelopment/electronic_applications/ctc.htm

- ^a Instrumental activities of daily living refer to preparing meals, shopping for groceries or clothes, using the telephone, managing money, etc.
- ^b Examples of self-care activities of daily living include bathing, dressing and undressing, feeding oneself, using the toilet, and taking medications, as performed by patients who are not bedridden.
- ^c If an event is assessed as a "significant medical event," it must be reported as a serious adverse event (see Section 5.4.2 for reporting instructions), per the definition of serious adverse event in Section 5.2.2.
- ^d Grade 4 and 5 events must be reported as serious adverse events (see Section 5.4.2 for reporting instructions), per the definition of serious adverse event in Section 5.2.2.

5.3.4 Assessment of Causality of Adverse Events

Investigators should use their knowledge of the patient, the circumstances surrounding the event, and an evaluation of any potential alternative causes to determine whether an adverse event is considered to be related to the trial treatment, indicating "yes" or "no" accordingly. The following guidance should be taken into consideration:

- Temporal relationship of event onset to the initiation of trial treatment
- Course of the event, with special consideration of the effects of dose reduction, discontinuation of trial treatment, or reintroduction of trial treatment (as applicable)
- Known association of the event with the trial treatment or with similar treatments
- Known association of the event with the disease under study
- Presence of risk factors in the patient or use of concomitant medications known to increase the occurrence of the event
- Presence of non-treatment-related factors that are known to be associated with the occurrence of the event

5.3.5 Procedures for Recording Adverse Events

Investigators should use correct medical terminology/concepts when recording adverse events on the Adverse Event eCRF. Avoid colloquialisms and abbreviations.

Only one adverse event term should be recorded in the event field on the Adverse Event eCRF.

5.3.5.1 Diagnosis versus Signs and Symptoms

A diagnosis (if known) should be recorded on the Adverse Event eCRF rather than individual signs and symptoms (e.g., record only liver failure or hepatitis rather than jaundice, asterixis, and elevated transaminases). However, if a constellation of signs and/or symptoms cannot be medically characterized as a single diagnosis or syndrome at the time of reporting, each individual event should be recorded on the Adverse Event eCRF. If a diagnosis is subsequently established, all previously reported adverse events based on signs and symptoms should be nullified and replaced by one adverse event report based on the single diagnosis, with a starting date that corresponds to the starting date of the first symptom of the eventual diagnosis.

5.3.5.2 Adverse Events That Are Secondary to Other Events

In general, adverse events that are secondary to other events (e.g., cascade events or clinical sequelae) should be identified by their primary cause, with the exception of severe or serious secondary events. A medically significant secondary adverse event that is separated in time from the initiating event should be recorded as an independent event on the Adverse Event eCRF. For example:

- If vomiting results in mild dehydration with no additional treatment in a healthy adult, only vomiting should be reported on the eCRF
- If vomiting results in severe dehydration, both events should be reported separately on the eCRF
- If a severe gastrointestinal hemorrhage leads to renal failure, both events should be reported separately on the eCRF
- If dizziness leads to a fall and consequent fracture, all three events should be reported separately on the eCRF
- If neutropenia is accompanied by an infection, both events should be reported separately on the eCRF

All adverse events should be recorded separately on the Adverse Event eCRF if it is unclear as to whether the events are associated.

5.3.5.3 Persistent or Recurrent Adverse Events

A persistent adverse event is one that extends continuously, without resolution, between patient evaluation time points. Such events should only be recorded once on the Adverse Event eCRF. The initial severity (intensity or grade) of the event will be recorded at the time the event is first reported. If a persistent adverse event becomes more severe, the most extreme severity should also be recorded on the Adverse Event eCRF. If the event becomes serious, it should be reported to the Sponsor immediately (i.e., no more than 24 hours after learning that the event became serious; see Section 5.4.2 for reporting instructions). The Adverse Event eCRF should be updated by

changing the event from "non-serious" to "serious," providing the date that the event became serious, and completing all data fields related to serious adverse events.

A recurrent adverse event is one that resolves between patient evaluation time points and subsequently recurs. Each recurrence of an adverse event should be recorded as a separate event on the Adverse Event eCRF.

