6.5 SAFETY ANALYSES

The safety analyses will include all randomized patients who received at least one dose of trial treatment, with patients grouped according to treatment received.

The safety objective for this trial is to evaluate the safety of pirfenidone vs. placebo (see Section 2).

The safety analysis will involve investigating the nature, frequency, severity, and timing of treatment-emergent adverse events. The specific parameters that will be investigated include all adverse events, adverse events Grade ≥ 3 according to the NCI CTCAE version 4.0, adverse events of special interest, and serious adverse events. The primary interest in this trial will be adverse events Grade ≥ 3 related to pirfenidone or placebo.

Prior to the first administration, only serious adverse events caused by a protocol-mandated intervention will be recorded. These adverse events will be listed.

The incidence, type, and severity of adverse events will be summarized according to the primary System Organ Class (SOC) and within each SOC, by the Medical Dictionary for Regulatory Activities (MedDRA) preferred term.

Adverse events Grade ≥ 3 , adverse events of special interest, and serious adverse events will be analyzed in a similar way to all adverse events.

Descriptive statistics will be presented for dose reductions and treatment interruptions. Adverse events leading to treatment interruption or dose reduction will also be summarized.

Laboratory parameters including hematology and the chemistry panel will be presented in shift tables of NCI-CTCAE version 4.0 grade at baseline versus worst grade during treatment period. The laboratory parameters will be presented according to means, standard deviation, minimum, and maximum. Selected laboratory parameters will be also graphically presented over time.

The results from the 12-lead ECGs will be summarized and presented.

The number of patients who withdraw from pirfenidone or placebo treatment with corresponding reason for withdrawal will be summarized and listed. The discontinuation from trial data will be also summarized and listed.

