4.6.2 Adverse Events

Verbatim descriptions of adverse events (AEs) will be mapped to a preferred term (PT) and system organ class (SOC) using the Medical Dictionary for Regulatory Agencies (MedDRA®). MedDRA version 20.1 or above and related SMQ lists will be used for coding.

AEs will be graded according to the National Cancer Institute Common Terminology Criteria for Adverse Events (NCI CTCAE), Version 4.03. For AEs of varying severity, the most severe grade as documented on the eCRF will be used in the summaries. An AE will be considered severe if the most extreme grade will be larger or equal to 3.

After informed consent has been obtained but prior to initiation of trial treatment, only serious adverse events caused by a protocol-mandated intervention (e.g. invasive procedures such as biopsies, discontinuation of medications) should be reported. All adverse events will be reported until 28 days after the last dose of study drug. After this period, the Investigator should report any SAEs that are believed to be related to prior study drug treatment.

For safety analysis of the double-blind treatment period treatment-emergent adverse events (TEAEs) will be defined as:

• AEs that started or worsened on or after first intake of randomized treatment until last positive dose of randomized treatment + 28 days

Adverse events that are reported after informed consent but before the first intake of randomized treatment will be considered as non-treatment-emergent AEs. These might include AEs that occur during the screening period.

Post-treatment AEs are not expected to occur, but will be defined as AEs that are reported more than 28 days after the last dose of randomized treatment for patients who do not enter the 12-month safety follow-up period. Those AEs will be listed.

Pirfenidone — F. Hoffmann-La Roche Ltd

The analysis of AEs within the framework of the primary study analysis will focus on treatment-emergent AEs (TEAE).

An overview of patient safety profile will present the number and proportion of patients in each treatment arm experiencing:

- Any and any related treatment-emergent adverse events (TEAE)
- Any and any related serious treatment-emergent adverse events (serious TEAE)
- Any and any related severe treatment-emergent adverse events (TEAEs ≥ Grade 3)
- Any and any related TEAE of special interest (AESI). Adverse events of special interest for this trial include the following:

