Non serious Treatment-emergent Adverse Events with >5% frequency will be also presented by SOC and PT. In addition, Serious Treatment-emergent Adverse Events, Fatal serious TEAEs and serious TEAEs related to pirfenidone or placebo will be presented in the same table by SOC and PT.

A summary table presenting the numbers and frequency of patients with TEAEs by most extreme CTCAE Grade (Grade 1, Grade 2, Grade 3, Grade 4 and Grade 5) will be provided for each SOC and PT by treatment arm. In case the most extreme intensity is missing, it will be replaced by the initial intensity. If both most extreme and initial intensity are missing, the AE will be included in the Grade ≥3 category and a category for "missing" will be added.

Further, Kaplan-Meier curves for time to onset of first adverse event of the most relevant related TEAEs will be provided by treatment arm when the number of events are enough to do the analyses. These will include the following PTs or groups of AEs: Nausea, Diarrhoea, Weight decreased, Fatigue, Decreased appetite, and photosensitivity, or rash. In addition, the analysis will be done for the SOC GI.

All adverse event data will be listed by patient number and study day of onset including a flag variable for identifying the period of the event (double-blind treatment period or safety follow-up period). If the AE does not belong to any of the periods, the period flag will be missing.

In addition, for regulatory purpose two additional tables will be provided:

Pirfenidone — F. Hoffmann-La Roche Ltd

Frequency of adverse drug reactions occurring in patients treated with Esbriet (Pirfenidone) in clinical trials

TEAEs from day 1 of dosing until 168 days for MA39189 will be compared with the data from the phase III studies CAPACITY1 and 2 and ASCEND (restricted to first 168 days after first dose). The frequency of patients with related AEs (ADR) will be presented by System Organ Class and will be classified by their occurrences into

- Very common ((>=10% incidence rate)
- common ((>= 1% to <10% incidence rate)
- uncommon (>= 0.1% to <1% incidence rate)
- rare (>= 0.01% to <0.1% incidence rate)

Patients who withdrew from treatment during first 168 days of dosing will be censored at day of withdrawal for this analysis.

Rates of Adverse events per 100 patient years

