4.7 SAFETY FOLLOW-UP ANALYSES

Data collected during the safety- follow-up period will be analyzed in the following way.

Adverse events during the 12-month safety follow-up period for pirfenidone treatment will be defined as:

 AEs that started or worsened on or after the date of safety follow-up period start until the end of the safety follow-up.

Pirfenidone — F. Hoffmann-La Roche Ltd

The safety follow-up population will be used for these analyses.

Summary tables for the incidence of AEs, related AEs, serious AEs, related serious AEs, severe AEs and severe related AEs will be summarized by system organ class (SOC) and preferred term (PT). Frequencies and percentages of patients experiencing (at least) one event in the respective category will be presented by decreasing frequencies. If patients have more than one AE within a SOC or PT they will be counted only once for the respective SOC or PT. Additionally, the total numbers of AEs will be provided for each SOC and overall. As with the end of the double-blind treatment period, an overview of safety will also be presented.

Pirfenidone exposure during safety-follow-up will be analyzed in a similar fashion as described in Section 4.7.1 with regard to treatment duration and amount of drug intake.

Data of laboratory assessments (AST, ALT, bilirubin, and alkaline phosphatase) and vital signs during safety-follow-up period will be analyzed in a similar fashion as described in Section 4.7.4 and Section 4.7.5.

Data will be presented by randomized treatment labeled as 'Randomized Pirfenidone' and 'Randomized Placebo'.

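### The double-blind adverse event tables take the most extreme grade from a record that can stay open into open-label pirfenidone, and no date of worsening is asked for to separate the two periods

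*Protocol*

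**What the plan says.** **Recording.** Protocol 5.3.5.3 on persistent events: "Such events should only be recorded once on the Adverse Event eCRF". On grade: "The initial severity (intensity or grade) of the event will be recorded at the time the event is first reported", and then "If a persistent adverse event becomes more severe, the most extreme severity should also be recorded on the Adverse Event eCRF". Nothing is said about when the grade rose. Seriousness is treated differently: the same record is switched to serious, with the investigator "providing the date that the event became serious".

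**Analysis.** In SAP version 3.0, section 4.6.2, an event is treatment-emergent in the double-blind period if it starts or worsens between the first randomised intake and 28 days after the last positive randomised dose. On grade, the section says: "For AEs of varying severity, the most severe grade as documented on the eCRF will be used in the summaries". One of its tables shows "the numbers and frequency of patients with TEAEs by most extreme CTCAE Grade" by treatment arm. Sections 2.2.4 and 4.2 limit double-blind safety analyses to the same window, and 4.2.5 keeps follow-up results separate. For the open-label period, SAP 4.7 counts "AEs that started or worsened on or after the date of safety follow-up period start".

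**Why grade matters here.** Protocol 6.5, repeated in SAP 4.6: "The primary interest in this trial will be adverse events Grade ≥ 3 related to pirfenidone or placebo".

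**The concern.** The window decides which events enter the double-blind tables. The grade given to each event is then read from a record that may have been updated well after the window closed. Both arms are offered open-label pirfenidone from the 28-day Follow-up Visit (Protocol 4.3.4), so a later grade may have been reached on a treatment the patient was not randomised to.

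The measure affected is the one the plan names as its main safety interest. A severe grade reached on open-label drug can be charged to placebo or to randomised pirfenidone. The same worsening may also be absent from the open-label tables, because the SAP 4.7 definition needs a date of worsening that the protocol does not request.

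**Working it through.** The plan gives no figure to reproduce on this point, so the check follows one event through the stated rules.

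1. *Can a record stay open across the switch?* Yes. Protocol 5.5.1 follows an event until it resolves to baseline grade or better, is judged stable, or follow-up ends. Open-label drug starts at the 28-day visit (Protocol 4.3.4).
2. *Can the later grade be in the database at analysis?* Yes. The primary cut-off waits for the last patient's 28-day visit (SAP 4.2.6), by which time earlier patients can be on open-label drug. The second cut-off comes after the full follow-up year.
3. *Trace.* A placebo patient has a Grade 1 event at Week 20. It does not resolve, and it reaches Grade 3 after open-label drug starts at Week 28. The record reads: initial Grade 1, most extreme Grade 3. Onset lies in the window, so the event is treatment-emergent. SAP 4.6.2 assigns Grade 3, and the patient enters the placebo Grade 3 or higher count.
4. *Does the window prevent this?* Sections 2.2.4 and 4.2 would exclude a grade reached after the window, but applying them needs the date of the increase. The grade rule in 4.6.2 carries no such limit.
5. *Does the open-label table pick it up?* SAP 4.7 would count it as worsened, but not from the fields Protocol 5.3.5.3 describes.
6. *Comparison inside the SAP.* For laboratory shift tables, SAP 4.6.4 confines the worst grade to the randomised double-blind period. For deaths, SAP 4.6.3 counts by date, up to 28 days after the last double-blind dose. The adverse event grade rule has no matching limit.

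**Size.** The documents give no rate for such events. Assume a safety population of about 125 per arm, the planned number. Change in an arm's Grade 3 or higher rate = 100 × m / 125 percentage points for m affected patients:

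| m (assumed) | Change (points) |
|---|---|
| 1 | 0.8 |
| 3 | 2.4 |
| 5 | 4.0 |
| 10 | 8.0 |

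The values of m show scale only. A patient counts towards m only if no other event already puts that patient in the same Grade 3 or higher cell. For the related-event table, the event must also be rated related.

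**The case against.** The strongest reply is that the SAP already bounds severity. Section 2.2.4 lists severity among the safety outcome measures and ties all their analyses to the double-blind window; 4.2 repeats the window. This stands as a statement of intent, and it rules out saying that the plan sets no time limit. It does not settle the matter, because the window cannot be applied to an undated grade and 4.6.2 gives a specific rule without reference to it.

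Second, the adverse event form itself is not in the documents. Protocol 5.3.5.3 is an instruction, not a field list, and the SAP's use of worsened presupposes that worsening can be dated. If the form does hold such a date, only the SAP wording needs repair. As written, neither document asks for one.

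Third, the scope is narrow. The event must start in the double-blind period, stay unresolved through the 28 days off drug, and worsen in a patient who enters the open-label period. New events, and events that resolve and recur, get their own records and are placed correctly. This stands.

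A reader might go further and infer that serious and fatal events are misplaced beyond repair. They are not: the date of becoming serious is collected and deaths are counted by date. A reader might also infer that placebo is hit harder, so that harm from pirfenidone is masked, since Protocol 5.1.1.2 says gastrointestinal events are most frequent in the first 3 months on drug. New gastrointestinal events after the switch have open-label onset and are assigned correctly, and patients randomised to pirfenidone are also re-exposed, with re-titration. The documents do not establish a net direction.

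**Conclusion.** The point holds for grade. One record, no requested date of worsening and an unqualified most-severe-grade rule together place a grade first reached on open-label pirfenidone in the randomised arm's double-blind table, placebo included. This is a stated rule that gives a wrong result for these events, not merely a missing detail.

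For seriousness and fatal outcome the gap is smaller: the dates exist, and the SAP need only say that they decide the period in the serious and fatal event tables.

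The size is 0.8 points per affected patient in an arm of about 125. How many patients are affected, and whether the difference between arms grows or shrinks, cannot be learned from the documents. The conclusion assumes that the form collects no more than Protocol 5.3.5.3 describes.

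**What to change.** 1. **SAP 4.6.2.** For double-blind tables, use the worst grade, seriousness and fatal outcome reached by the earlier of two dates: last positive randomised dose plus 28 days, or first open-label dose. Use the recorded date of becoming serious and the date of death. The earlier-of rule is needed because Appendix 1 allows the Follow-up Visit ±5 days, so open-label drug can start up to 5 days before the 28 days are complete.
2. **Protocol 5.3.5.3 and eCRF.** Record the date of a grade increase, or the worst grade in each period. SAP 4.5.8 places the primary analysis in March 2019, so for data already collected query only events that were ongoing at the first open-label dose and whose most extreme grade exceeds the initial grade.
3. **SAP 4.7.** Count as worsened in the open-label period any event whose grade or seriousness rises above its status at the first open-label dose.
4. **Date not recoverable.** Keep the most extreme grade in the main table and add a sensitivity table using the initial grade, so that both bounds are visible. The initial grade should not be the main analysis: it would downgrade events that truly reached Grade 3 on randomised pirfenidone and were still ongoing at the switch.

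The cost is a small number of data queries, one date field and minor reprogramming.
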